6. ASSESSMENT AND FOLLOW-UP

6.1 Recruitment

Recruitment will be undertaken in endocrinology and diabetes clinics at Imperial College Healthcare NHS Trust. Participant information sheets will be given to potential subjects and, following any questions, informed consent will be taken. We will identify potential participants from medical records and post/email them a copy of the Patient Information Sheet (PIS) prior to approaching them in clinic.

Participants will be given as much time as they require (and at least 24 hours) to decide whether or not to take part – this can vary on a per participant basis.

6.2 Enrolment and study conduct

6.2.1 Visit 1: Baseline Screening

(Day 0, to last approximately 2 hours)

Participants will attend an initial screening visit at the NIHR Imperial College Research Facility (ICRF). Following informed consent, the research team will collect full medical and medication history and conduct routine anthropometry (height and weight). The research team will also carry out a physical examination including a general chest examination and abdominal examination (auscultation of lungs, heart and abdomen and palpation of the chest wall and abdomen). Participants will be asked to provide a urine sample (urine albumin:creatinine ratio) and a venous blood sample will be taken (full blood count, HbA1c, urea, creatinine and electrolytes, thyroid function, c-peptide and glucose). We will measure baseline steroid replacement with serum prednisolone levels or hydrocortisone day curves (see appendix 2). Blood samples will be sent to the accredited Imperial College Healthcare NHS Trust laboratory for analysis. Urine pregnancy tests will be done in females of childbearing age. Urine and blood samples will not be stored. Participants will complete the Gold questionnaire to assess for hypoglycaemia awareness, the Hyperglycaemic Fear Survey-II and Hospital Anxiety and Depression Survey. All questionnaires used are validated.

Participants will be provided with a continuous glucose monitoring (CGM) device. The system continuously measures glucose levels in interstitial fluid through a small sensor which is inserted under the skin. For the control group, the device will be blinded to the participant. In participants who have insulin-treated diabetes, the data can be read on a display device (receiver) or a compatible smart app. Each participant will have a sensor fitted in clinic. They will be given education for use of the device according to the manufacturer's guidelines. They will have access to the Dexcom G6 User Guide, which is available online. Participants will be shown how to insert the sensors themselves and provided with adequate sensors and transmitters for the duration of the trial. If the participants' sensor fails or falls out the research team will provide a new sensor. Participants will be instructed to test their glucose as per standard care, and to manage as their usual care if symptoms of hypo- or hyperglycaemia occur. Refresher education regarding general diabetes management and management of hypoglycaemia specifically will be offered.

Participants will be supported to change their glucose sensor every 10 days at home. Those with unblinded devices will be given education and support to manage the alerts

and alarms provided by the system. At this visit the glucose threshold low alert will be set to 4.4 mmol/L and the high threshold alert will be set to 12mmol/L. These can be personalised by participants throughout the study to manage alert burden. Participants will have access to a helpline for any queries or concerns regarding their device.

6.2 Visit 2: Final Study Visit

(Day 30, to last approximately 1 hour)

Participants will attend the ICRF 30 days after their baseline screening for data collection. Participants will be invited to review and discuss the data collected with a clinician. This review may be conducted over the telephone as per the participant's preference.

All study equipment will be returned, and participants will return to standard care.

6.3 End of Study

End of study will be defined as Last Subject Last Visit (LSLV)

6.3.1 Incidental findings

Incidental findings identified from laboratory investigations during the study will be reviewed by the investigators and will then be communicated by the study team to the participant and to the participant's GP.

Incidental findings identified from laboratory investigations during the study will be reviewed by the investigators and will then be communicated by the study team to the participant and to the participant's GP with a clear management plan.

Examples of potential incidental findings include:

1. A new diagnosis of pre-diabetes or diabetes in the control group

2. Hypothyroidism (underachieve thyroid) or hyperthyroidism (overactive thyroid)

3. Anaemia

7. STATISTICS AND DATA ANALYSIS

This is a pilot study and therefore we are not proposing a fully-powered study (4). The data gathered from the proposed work will serve as robust pilot data to support a larger randomised study.

The primary outcome is the percent time spent with glucose below 3.0mmol/L. This is in accordance with international consensus for hypoglycaemia. Glucose data will be extracted from the 30 days of unblinded/blinded CGM and used for analysis.

A two-tailed unpaired t-test will be performed to compare the primary and secondary glucose outcomes between groups. A p-value of <0.05 will be considered statistically significant.

All study data including personal and pseudoanonymised data and all appropriate documentation will be stored for a minimum of 5 years after the completion of the study, including the follow-up period.

8. REGULATORY ISSUES

ETHICS APPROVAL

The Study Coordination Centre has obtained approval from the xxx Research Ethics Committee (REC) and Health Research Authority (HRA). The study must also receive confirmation of capacity and capability from each participating NHS Trust before accepting participants into the study or any research activity is carried out. The study will be conducted in accordance with the recommendations for physicians involved in research on human subjects adopted by the 18th World Medical Assembly, Helsinki 1964 and later revisions.

CONSENT

Consent to enter the study must be sought from each participant only after a full explanation has been given, an information leaflet offered and time allowed for consideration. Signed participant consent should be obtained. The right of the participant to refuse to participate without giving reasons must be respected. After the participant has entered the study the clinician remains free to give alternative treatment to that specified in the protocol at any stage if he/she feels it is in the participant's best interest, but the reasons for doing so should be recorded. In these cases the participants remain within the study for the purposes of follow-up and data analysis. All participants are free to withdraw at any time from the protocol treatment without giving reasons and without prejudicing further treatment.

CONFIDENTIALITY

Pseudonymised data is data that can be linked back to a person (e.g. coded data). It is considered both personal and identifiable data. Anonymised data is data that has no code and cannot be linked back to a person (e.g. aggregated data for publication, data without a code that cannot be linked back to a person)

The Chief Investigator will preserve the confidentiality of participants taking part in the study and is registered under the Data Protection Act.

Data will be pseudonymised

Dexcom is a separate data controller and is able to access pseudoanonymised CGM data from Dexcom device users. They have a separate privacy notice and subject rights which can be accessed online here: https://www.dexcom.com/en-GB/linked/documentservice/PrivacyPolicy.

INDEMNITY

Imperial College Healthcare NHS Trust holds standard NHS Hospital Indemnity and insurance cover with NHS Resolution for NHS Trusts in England, which apply to this study

SPONSOR

Imperial College Healthcare NHS Trust will act as the main Sponsor for this study. Delegated responsibilities will be assigned to the NHS trusts taking part in this study.

FUNDING

The Imperial Health Charity are funding this study.

AUDITS

The study may be subject to audit by Imperial College Healthcare NHS Trust under their remit as sponsor and other regulatory bodies to ensure adherence to GCP and the UK Policy Frame Work for Health and Social Care Research.

9. STUDY MANAGEMENT

The day-to-day management of the study will be co-ordinated through [name].

10. PUBLICATION POLICY

The study will be registered on the clinicaltrials.gov system and results will be disseminated by peer reviewed scientific journals, internal report, conference presentation and publication on websites. No identifiable personal data will be published. All anthropometry and personal clinical data will be expressed as mean/ median and spread of the population in the study. Details of any publications that arise from the study will be disseminated to participants on request.

Appendix 1. Summary of activities at and between visits

	VISIT 1			VISIT 2
	Day 0	Day 10	Day 20	Day 30
Medical history	Х			
Medication history	Х			
Physical examination	х			
Pregnancy test (urine)	x			
Full Blood Count	х			
Renal Function	х			
HbA1c	х			
TFT	х			
C peptide	х			
Glucose	х			
Cortisol day curve/ Prednisolone level	X			
Gold score	х			
QoL questionnaires	х			
CGM education	Х			
CGM insertion (supervised	х			
by research team)				
CGM insertion (independently by		x	x	
participant				
CGM download	X			X
Data review				Х

Appendix 2. Protocols for baseline steroid measurement

Prednisolone Level

Preparation

- Stop all oestrogen therapy 6 weeks prior to test.
- No need to fast.
- Take normal morning prednisolone and patient should note down actual time taken.

Method

A sample is taken 8h following the administration of prednisolone. If the dose was taken at 7am at home, the final sample should be taken at 3pm.

Hydrocortisone Day Curve

Preparation

- Stop all oestrogen therapy 6 weeks prior to test.
- No need to fast.
- Take normal morning hydrocortisone and patient should note down actual time taken.
- Equipment required: 18-20g cannula. Red or yellow top Vacutainers. Syringes.

Method

Take blood at the following times:

- 1. Blood sample on arrival, noting time of sample and time and dose of hydrocortisone.
- 2. Pre lunchtime (2nd) dose
- 3. 1 hour post lunchtime (2nd) dose
- 4. pre evening (3rd) dose
- 5. post evening (3rd) dose or at 6pm.

Source: Endocrinology Handbook. Imperial Centre for Endocrinology. Imperial College Healthcare NHS Trust. Latest edition February 2018. Bible2018.pdf (imperialendo.co.uk)

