3. STUDY DESIGN

This is a prospective observational study in 16 adults with both insulin-treated diabetes and adrenal insufficiency and 16 age, sex and steroid replacement matched controls without diabetes. We will recruit and enrol 32 participants in total. Participants will spend 30 days in the study.

STUDY OUTCOME MEASURES

Primary outcomes: Percentage time spent with glucose below 3.0mmol/L

Secondary outcomes: Percentage time spent with glucose below 3.9mmol/L, between 3.9mmol/L and 10mmol/L, and above 10mmol/L. Number of episodes of hypoglycaemia and severe hypoglycaemia. Outcomes will be retrieved for the nocturnal period (midnight to 6am) and separately for the 24-hour period. Gold score, Hyperglycaemia Fear Survey-II (HFS-II) score and Hospital Anxiety and Depression (HADS) Score.

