4. PARTICIPANT ENTRY

INCLUSION CRITERIA

- for test group:

Confirmed diagnoses of adrenal insufficiency and insulin-treated diabetes for more than one year.

Adults aged above 18 years

-for matched control group:

Diabetes mellitus excluded on baseline blood review Adults aged above 18 years

EXCLUSION CRITERIA

Measured eGFR ≤ 30 Acute illness Abnormal thyroid function Admission to hospital Pregnant or planning pregnancy Breastfeeding Enrolled in other clinical trials, except at the discretion of the chief investigator Have active malignancy or under investigation for malignancy Severe visual impairment Reduced manual dexterity Unable to participate due to other factors, as assessed by the Chief Investigators

WITHDRAWAL CRITERIA

The subject has a serious event related to study Investigator initiated discontinuation of study due to participation or equipment concerns Withdrawal of consent

<70% complete continuous glucose monitoring (CGM) data within 10 day run in period

Withdrawal will be immediate. Identifiable data already collected with consent will be retained and used in the study. No further data would be collected or any other research procedures carried out on or in relation to the participant.

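### Appendix 2 requires oestrogen to be stopped 6 weeks before a steroid test held only on Day 0, but nothing before Day 0 identifies users, times their consent or arranges a restart

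*Protocol*

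**What the plan says.** Section 6.2.1 of the protocol (Visit 1, Day 0) states: "We will measure baseline steroid replacement with serum prednisolone levels or hydrocortisone day curves (see appendix 2"). Appendix 2 gives one test protocol for prednisolone and one for hydrocortisone. Each opens its preparation list with the same unconditional line: "Stop all oestrogen therapy 6 weeks prior to test". The row "Cortisol day curve/ Prednisolone level" in Appendix 1 has a single mark, under Day 0.

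The rest of the timetable is as follows.

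- **Length (Section 3):** "Participants will spend 30 days in the study".
- **Final visit (Section 6.2, Visit 2):** "Participants will attend the ICRF 30 days after their baseline screening for data collection".
- **Recruitment (Section 6.1):** "We will identify potential participants from medical records and post/email them a copy of the Patient Information Sheet (PIS") before an approach in clinic. Candidates have as long as they need to decide, with a minimum of 24 hours.
- **Medication history (Section 6.2.1):** "Following informed consent, the research team will collect full medical and medication history". Appendix 1 also places this on Day 0.
- **Exclusions (Section 4):** the list includes "Acute illness Abnormal thyroid function Admission to hospital Pregnant or planning pregnancy Breastfeeding Enrolled in other clinical trials", but neither this run nor the rest of the list mentions oestrogen.

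Oestrogen appears nowhere in the protocol outside Appendix 2.

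**The concern.** The protocol takes on a preparation step that must begin six weeks before Day 0, but no activity before Day 0 is designed to deliver it. Staff who reach Visit 1 with an oestrogen user have two options. They can run the test without the preparation that the protocol's own procedure demands. Or they, or someone before them, can have stopped a prescribed medicine about six weeks earlier, at a point where the protocol schedules neither consent nor a check and after which it gives no restart.

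The instruction covers all oestrogen therapy and makes no exception for contraceptive use. Yet pregnancy and planned pregnancy are exclusions, and the only pregnancy test in Appendix 1 is on Day 0. The study is described as observational, so a participant would not expect to have a regular medicine withdrawn for it. What is at stake is participant safety and burden, and whether baseline steroid levels in oestrogen users were obtained under the stated conditions.

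**Working it through.** The check is calendar arithmetic combined with a search of the timetable for a step that could deliver the stop.

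**Inputs.** Oestrogen stop: 6 weeks before the test (Appendix 2). Test day: Day 0 only (Section 6.2.1, Appendix 1). Final visit: Day 30 (Section 6.2, Visit 2). Stated participation: 30 days (Section 3). Minimum time to decide: 24 hours (Section 6.1). First medication history: Day 0 (Section 6.2.1).

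**The plan's own figure.** Day 30 − Day 0 = 30 days, which agrees with Section 3.

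**Date of the stop.** 6 × 7 = 42 days, so oestrogen must stop by 0 − 42 = Day -42.

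**Can any described step deliver it?**

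1. *Section 6.1.* The records search, information sheet and clinic approach all come before Visit 1, but none mentions oestrogen. The only guaranteed interval is 1 day, and 42 − 1 = 41 days short.
2. *Visit 1 medication history.* If use first comes to light on Day 0, the earliest compliant test is Day 0 + 42 = Day 42, which is 42 − 30 = 12 days after the final visit. Appendix 1 has no such slot.
3. *The 10-day run-in in the Section 4 withdrawal criteria.* This concerns completeness of the glucose-monitoring data. The sensor is fitted at Visit 1, so the run-in follows Day 0 and is not an oestrogen lead-in.
4. *Exclusion.* None applies, so users can enrol.

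**Time off oestrogen.** If it restarts straight after the Day 0 test, 42 days is the minimum. No maximum is stated. If the general return to standard care at Visit 2 were read as the restart, the time off would be 42 + 30 = 72 days.

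**Involvement of a user who complies.** Day -42 to Day 30 = 72 days, against the 30 stated.

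**Reach.** The study plans 32 participants (16 with diabetes, 16 controls). The protocol does not give the number taking oestrogen.

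**The case against.** The strongest reply is that this is an unwritten detail rather than a contradiction. Preparation for a test naturally comes before the test visit, and nothing requires it to fall within the 30 days. Section 6.1 sets no upper limit on the time between first approach and Visit 1, and it allows consent in clinic, so a six-week stop after clinic consent is possible. Candidates are found from medical records, so the team may already know who takes oestrogen. The participant information sheet is not available here and could carry an instruction. Appendix 2 cites the Trust's own endocrinology handbook and reads like routine clinical test instructions, under which restarting a paused medicine would be ordinary clinical care.

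Much of this stands. A reader might infer that a 42-day stop cannot fit a 30-day study, or that the ratio 42/30 = 1.4 measures the problem. The documents do not support that: the 30 days run forward from Day 0 and the stop runs backward from it, so the same gap would exist with any length of follow-up. Nor is the stop shown to be impossible.

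The reply does not show that following the protocol delivers the preparation. Section 6.2.1 makes Appendix 2 part of study conduct, whatever its origin. No described step asks about oestrogen before Day 0, sets consent six weeks ahead or arranges the restart, and the protocol points to no other document that does.

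**Conclusion.** The point holds as a minor safety and feasibility gap. The protocol fixes a stop on about Day -42 and a test on Day 0, but provides no oestrogen check, no consent timed at least 42 days ahead and no restart. The textual gap is certain; its practical consequences are less so. They depend on how many participants take oestrogen, which is unknown and may be zero, and on the assumption that no instruction in the unseen information sheet fills the gap.

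Two further inferences should be resisted. The first is that the trial's results are compromised. The steroid level is neither a listed outcome (Section 3) nor an eligibility criterion (Section 4), and the primary outcome, time with glucose below 3.0 mmol/L, does not use it. The second is that the stop should simply be deleted. The protocol does not say why the stop is required, and nothing in it shows that levels measured on oestrogen are interchangeable with the rest, so the documents do not support removing it for everyone.

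**What to change.** In Section 6.1 and Appendix 1, add an oestrogen check at recruitment. For users who agree to stop, require consent at least 6 weeks before Day 0, state that oestrogen restarts straight after the Day 0 test, and give their longer involvement (72 days from stop to final visit) alongside the 30 days in Section 3. If a user should not or does not wish to stop, do not stop the oestrogen. Record its use in the Visit 1 medication history and flag that participant's steroid level as measured on oestrogen. Add a cross-reference in Appendix 2 so that its preparation lines are read with this rule.

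The cost is a wording amendment, one question at recruitment and one data field in a history already taken. The downsides are a later Day 0 for the few users who stop, and less comparable baseline steroid levels for those who do not.
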